8.1 Definitions

Unanticipated Problems Involving Risk to Subjects or Others

For the current study, we will use CTCAE criteria, incorporating the additional considerations about pediatric effects and regarding hospitalization. Any incident, experience, or outcome that meets all of the following criteria:

- Unexpected in nature, severity, or frequency (i.e. not described in study-related documents such as the IRB-approved protocol or consent form, the investigators brochure, etc.)
- Related or possibly related to participation in the research (i.e. possibly related means there is a reasonable possibility that the incident experience, or outcome may have been caused by the procedures involved in the research)

CONFIDENTIAL

This material is strictly confidential and is intended solely for the guidance of clinical investigation. Do not disclose or use except as authorized in writing by the study sponsor

- Suggests that the research places subjects or others at greater risk of harm (including physical, psychological, economic, or social harm).

Adverse Event

An **adverse event** (AE) is any symptom, sign, illness or experience that develops or worsens in severity during the course of the study. Intercurrent illnesses or injuries should be regarded as adverse events. Abnormal results of diagnostic procedures are considered to be adverse events if the abnormality:

- results in study withdrawal
- is associated with a serious adverse event
- is associated with clinical signs or symptoms
- leads to additional treatment or to further diagnostic tests
- is considered by the investigator to be of clinical significance

Serious Adverse Event

Adverse events are classified as serious or non-serious. A **serious adverse event** is any AE that is:

- fatal
- life-threatening
- requires or prolongs hospital stay
- results in persistent or significant disability or incapacity
- a congenital anomaly or birth defect
- an important medical event

Important medical events are those that may not be immediately life threatening, but are clearly of major clinical significance. They may jeopardize the subject, and may require intervention to prevent one of the other serious outcomes noted above. For example, drug overdose or abuse, a seizure that did not result in in-patient hospitalization, or intensive treatment of bronchospasm in an emergency department would typically be considered serious.

All adverse events that do not meet any of the criteria for serious should be regarded as **non-serious adverse events**.

Adverse Event Reporting Period

The study period during which adverse events must be reported is normally defined as the period from the initiation of any study procedures to the end of the study treatment follow-up. For this study, the study treatment follow-up is defined as 30 days following the last administration of study treatment.

Preexisting Condition

A preexisting condition is one that is present at the start of the study. A preexisting condition should be recorded as an adverse event if the frequency, intensity, or the character of the condition worsens during the study period.

General Physical Examination Findings

At screening, any clinically significant abnormality should be recorded as a preexisting condition. At the end of the study, any new clinically significant findings/abnormalities that meet the definition of an adverse event must also be recorded and documented as an adverse event.

Post-study Adverse Event

All unresolved adverse events should be followed by the investigator until the events are resolved, the subject is lost to follow-up, or the adverse event is otherwise explained. At the last scheduled visit, the investigator should instruct each subject to report any subsequent event(s) that the subject, or the subject's personal physician, believes might reasonably be related to participation in this study. The investigator should notify the study sponsor of any death or adverse event occurring at any time after a subject has

CONFIDENTIAL

This material is strictly confidential and is intended solely for the guidance of clinical investigation. Do not disclose or use except as authorized in writing by the study sponsor

discontinued or terminated study participation that may reasonably be related to this study. The sponsor should also be notified if the investigator should become aware of the development of cancer or of a congenital anomaly in a subsequently conceived offspring of a subject that has participated in this study.

Abnormal Laboratory Values

A clinical laboratory abnormality should be documented as an adverse event if any one of the following conditions is met:

- The laboratory abnormality is not otherwise refuted by a repeat test to confirm the abnormality
- The abnormality suggests a disease and/or organ toxicity
- The abnormality is of a degree that requires active management; e.g. change of dose, discontinuation of the drug, more frequent follow-up assessments, further diagnostic investigation, etc.

Hospitalization, Prolonged Hospitalization or Surgery

For the current study, we will use CTCAE criteria, incorporating the additional considerations about pediatric effects and regarding hospitalization. Any adverse event that results in hospitalization or prolonged hospitalization should be documented and reported as a serious adverse event unless specifically instructed otherwise in this protocol. Any condition responsible for surgery should be documented as an adverse event if the condition meets the criteria for an adverse event.

Neither the condition, hospitalization, prolonged hospitalization, nor surgery are reported as an adverse event in the following circumstances:

- Hospitalization or prolonged hospitalization for diagnostic or elective surgical procedures for a preexisting condition. Surgery should **not** be reported as an outcome of an adverse event if the purpose of the surgery was elective or diagnostic and the outcome was uneventful.
- Hospitalization or prolonged hospitalization required to allow efficacy measurement for the study.
- Hospitalization or prolonged hospitalization for therapy of the target disease of the study, unless it is a worsening or increase in frequency of hospital admissions as judged by the clinical investigator.

Expected and Unexpected event criteria

Side effects of megestrol affect up to 5% of adults and older children. Those expected side effects include:

- Diarrhea
- Rash
- Gas
- High blood pressure
- Weakness
- Trouble sleeping
- Nausea
- Low levels of oxygen in the blood causing pall skin color and sleepiness
- Adrenal insufficiency (pale skin color, cold to the touch, weight loss, thirsty, dizzy or disoriented)
- Fever
- Stomach pain and discomfort
- Heartburn
- High levels of sugar in the blood, which can cause tiredness, blurry vision, increased thirst and hunger, and passing urine often.
- Headache
- Pain
- Vomiting
- Pneumonia
- Urinary Frequency

CONFIDENTIAL

This material is strictly confidential and is intended solely for the guidance of clinical investigation. Do not disclose or use except as authorized in writing by the study sponsor

All events (expected or unexpected) will be logged and reported to the lead PI, [name] and the Medical Monitor, [name]. Side effects other than those listed above would be considered unexpected and would be also reported to the IRB. If an expected event is happening at a higher rate than anticipated (>5% of patients), the IRB must also be notified.

If medical or psychosocial concerns occur during week 1-9 that do not meet the criteria for subject withdraw, but negatively affect the subject's feeding routine, the PI and the Medical Monitor may pause the protocol until the patient regains feeding stability. The subject will resume the protocol if the feeding interruption is short-term (2 weeks to 6 months). For long-term feeding interruptions (>6 months), the subject may start the protocol over at week 0.

8.2 Recording of Adverse Events

At each contact with the subject, the investigator must seek information on adverse events by specific questioning and, as appropriate, by examination. Information on all adverse events should be recorded immediately in the source document, and also in the appropriate adverse event module of the case report form (CRF). All clearly related signs, symptoms, and abnormal diagnostic procedures results should be recorded in the source document, though should be grouped under one diagnosis.

All adverse events occurring during the study period must be recorded. The clinical course of each event should be followed until resolution, stabilization, or until it has been determined that the study treatment or participation is not the cause. Serious adverse events that are still ongoing at the end of the study period must be followed up to determine the final outcome. Any serious adverse event that occurs after the study period and is considered to be possibly related to the study treatment or study participation should be recorded and reported immediately.

8.3 Reporting of Serious Adverse Events and Unanticipated Problems

Investigators and the protocol sponsor must conform to the adverse event reporting timelines, formats and requirements of the various entities to which they are responsible, but at a minimum those events that must be reported are those that are:

- related to study participation,
- unexpected, and
- serious or involve risks to subjects or others
(see definitions, section 8.1).

If the report is supplied as a narrative, the minimum necessary information to be provided at the time of the initial report includes:

• Study identifier• Study Center• Subject number• A description of the event• Date of onset	
• Current status• Whether study treatment was discontinued• The reason why the event is classified as serious• Investigator assessment of the association between the event and study treatment
---	--

8.3.1 Investigator reporting: notifying the investigator sponsor

Any study-related unanticipated problem posing risk of harm to subjects or others, and any type of serious adverse event, must be reported to [name] by telephone within 24 hours of the event. To report such events, a Serious Adverse Event (SAE) form must be completed by the investigator and faxed to the study sponsor within 24 hours. The investigator will keep a copy of this SAE form on file at the study site. Report serious adverse events by phone and facsimile to: [name], MPH, ABPP (email, [contact], [contact], [contact] or 24 hours [contact]).

Within 48 hours of the report, the investigator must provide further information on the serious adverse event or the unanticipated problem in the form of a written narrative. This should include a copy of the completed

CONFIDENTIAL

This material is strictly confidential and is intended solely for the guidance of clinical investigation. Do not disclose or use except as authorized in writing by the study sponsor

Serious Adverse Event form, and any other diagnostic information that will assist the understanding of the event. Significant new information on ongoing serious adverse events should be provided promptly to the study sponsor.

8.3.2 Investigator reporting: notifying the IRB

Investigators are responsible for safety reporting to their local IRB. Investigators are responsible for complying with their local IRB's reporting requirements, though must submit the required reports to their IRB no later than 5 working days. Copies of each report and documentation of IRB notification and receipt will be kept in the investigator's study file.

Other Reportable events:

For clinical drug trials, the following events are also reportable to the IRB:

- Any adverse experience that, even without detailed analysis, represents a serious unexpected adverse event that is rare in the absence of drug exposure (such as agranulocytosis, hepatic necrosis, Stevens-Johnson syndrome).
- Any adverse event that would cause the sponsor to modify the investigators brochure, protocol or informed consent form, or would prompt other action by the IRB to assure protection of human subjects.
- Information that indicates a change to the risks or potential benefits of the research, in terms of severity or frequency. For example:
 - An interim analysis indicates that participants have a lower rate of response to treatment than initially expected.
 - Safety monitoring indicates that a particular side effect is more severe, or more frequent than initially expected.
 - A paper is published from another study that shows that an arm of your research study is of no therapeutic value.
- Breach of confidentiality
- Change to the protocol taken without prior IRB review to eliminate apparent immediate hazard to a research participant.
- Incarceration of a participant when the research was not previously approved under Subpart C and the investigator believes it is in the best interest of the subject to remain on the study.
- Complaint of a participant when the complaint indicates unexpected risks or the complaint cannot be resolved by the research team.
- Protocol violation (meaning an accidental or unintentional deviation from the IRB approved protocol) that in the opinion of the investigator placed one or more participants at increased risk, or affects the rights or welfare of subjects.

The following describes the safety reporting requirements by timeline for reporting and associated type of event:

- ***Within 7 calendar days***

Any study event that is:

- associated with the use of the study drug
- unexpected,
- fatal or life-threatening, and

- ***Within 15 calendar days***

Any study event that is:

- associated with the use of the study drug,
- unexpected, and
- serious, but not fatal or life-threatening

-or-

CONFIDENTIAL

This material is strictly confidential and is intended solely for the guidance of clinical investigation. Do not disclose or use except as authorized in writing by the study sponsor

- a previous adverse event that was not initially deemed reportable but is later found to fit the criteria for reporting (reporting within 15 calendar days from when event was deemed reportable).

Any finding from tests in laboratory animals that:

- suggest a significant risk for human subjects including reports of mutagenicity, teratogenicity, or carcinogenicity.

8.3.3 Sponsor reporting: Notifying participating investigators

It is the responsibility of the study sponsor to notify all participating investigators of any adverse event associated with the use of the drug that is both serious and unexpected, as well as any finding from tests in laboratory animals that suggest a significant risk for human subjects.

8.4 Unblinding Procedures

Each investigator must inform the sponsor of all subjects whose treatment was unblinded within 24 hours of such unblinding. We anticipate that in most cases, the unblinding will be part of managing an SAE, and will be reported with the SAE, however, in cases where unblinding was not associated with an SAE, such actions should be reported within one week.

At the completion of the study, participants will be contacted to notify them of their treatment assignment.

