6.11 Clinic Visit 4 (Week 24)

Participants will return to clinic to complete vital signs and measures (PIP, ITQOL or CHQ, RAND SF-36, PedsQL) and schedule three 24 hr Dietary recall phone calls over the coming week. Participants will bring in a frozen stool sample. Families will be encouraged to contact team members with questions or concerns at any time throughout the study period.

At every clinic visit and tele-visit we will record and evaluate concomitant medications. Also, if any safety concerns are noted at any clinic or tele-visit, additional visits may occur. Should any clinical concerns be noted, appropriate medical/clinical treatments will also occur as necessary. If any serious adverse events occur (as outlined elsewhere), providers will be unblinded to the subject's group, the subject will be removed from the study and patients will receive all necessary treatment clinically.

7 Statistical Plan

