8.5 Stopping Rules

If 2 out of the first 20 patients have a grade 3 event related to the study, we will stop or modify the study; if 1 subject has a grade 4 event related to the study, we will stop the study. After a stop the study will only restart after a thorough review and uniform agreement by the investigators and the DSMB.

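### Providers are unblinded at any SAE and nothing requires grade or relatedness to be recorded first, so once dosing has started relatedness may be judged knowing the arm

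*Combined protocol and SAP*

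**What the plan says.** Four parts of the protocol bear on this.

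- **Unblinding.** Section 6.11 says: "If any serious adverse events occur (as outlined elsewhere), providers will be unblinded to the subject's group, the subject will be removed from the study". It attaches no condition that the arm be needed for care. Section 8.4 adds: "We anticipate that in most cases, the unblinding will be part of managing an SAE, and will be reported with the SAE".
- **Relatedness.** Section 8.3 states that, for a report supplied as a narrative, "the minimum necessary information to be provided at the time of the initial report includes" a list of items, one of which is: "Investigator assessment of the association between the event and study treatment".
- **Timing.** Section 8.3.1 says that "a Serious Adverse Event (SAE) form must be completed by the investigator and faxed to the study sponsor within 24 hours". It continues: "Within 48 hours of the report, the investigator must provide further information on the serious adverse event", in the form of a written narrative.
- **Use of the judgement.** Section 8.5 counts grade 3 events related to the study (2 in the first 20 patients leads to a stop or modification), and for grade 4: "if 1 subject has a grade 4 event related to the study, we will stop the study". Section 8.3.2 sets the 7- and 15-day reports for unexpected events associated with the study drug, and 8.3.3 uses association with the drug to decide which events go to participating investigators.

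Sections 5.3 and 5.6 describe blinding differently from 6.11. They present the site pharmacy as the only unblinded part of the team, apart from the statistician who generates the codes. Neither makes an exception for SAEs.

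**The concern.** Causality attribution is a judgement, and it is most easily swayed when an event has several plausible explanations. Section 8.1 lists fever, vomiting, diarrhea, stomach pain and pneumonia among the expected effects of megestrol. These are also plausible intercurrent events in children whom section 3.3 describes as medically complicated. For an ambiguous admission, knowing whether the child received megestrol or placebo could decide the answer.

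The answer has consequences. One related grade 4 event stops the trial, so a single attribution can be decisive. Expedited reporting turns on the same kind of judgement. The trial's stated purpose includes weighing the risk of megestrol against its benefit, and a list of related events judged with the arm known would be weak evidence for that. An opinion formed with the arm known cannot later be converted into a masked one.

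**Working it through.** The plan gives no figure that depends on this point: no assumed SAE rate, no relatedness rate and no operating characteristics for the stopping rules. The check is therefore a reading of the sections side by side.

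1. **Which SAEs are unblinded?** Section 6.11 covers any SAE. Section 8.4 does not establish this: it says that most unblindings will arise from SAEs, which is not the same as every SAE being unblinded. The support is 6.11.

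2. **When is relatedness recorded relative to the code break?** The SAE form is due within 24 hours of the event and the narrative within 48 hours of the report. The causality item belongs to the initial narrative report (8.3), and the unblinding is expected to be reported with the SAE (8.4). Both fall in the same reporting window, and no section puts one before the other.

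3. **Is there a masked assessor?** None is named. Section 8.6 has the medical monitor review all reported adverse events but gives that role no stated blinding status and no causality task. Masking of the monitor is implied only by 5.3 and 5.6. If the unblinding is reported with the SAE, the monitor could receive the arm too.

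4. **Which SAEs matter?** Children are randomized after the week 0 visit (6.2), but the first dose follows the week 10 visit, once the morning cortisol is confirmed normal (6.4). Before the first dose, the arm has no bearing on drug causality. The gap concerns SAEs from the start of dosing.

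5. **Which stopping-rule events are reached?** Unblinding in 6.11 is tied to seriousness, which 8.1 defines by outcome. Section 8.5 is tied to grade. Only events that meet both criteria are exposed. Section 8.1 refers to CTCAE criteria but does not map grade to seriousness, so the overlap cannot be counted.

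6. **Can a size or direction be given?** Let each arm contribute n children with the same event rate q, and let a and b be the probabilities that an event is called related in the megestrol and placebo arms.
   - Expected related events in total = nq(a + b). Difference between arms = nq(a − b).
   - Masked, a = b = r: total 2nqr, difference 0.
   - Knowing the arm moves both, a = r + d and b = r − d: total 2nqr, unchanged; difference 2nqd.
   - Only the megestrol arm moves, a = r + d and b = r: total 2nqr + nqd, higher.
   - Only the placebo arm moves, a = r and b = r − d: total 2nqr − nqd, lower.

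   The expected total feeding the stopping rule can rise, fall or stay the same, while the by-arm split is distorted in all three cases. The documents give no value for q, r or d, so neither sign nor size follows from them.

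**The case against.** A reader might infer from 6.11 and 8.4 that relatedness is always judged with the arm known, and that the stopping rules are biased as a result. The documents do not support that.

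- **The order is left open.** No section says that assessment follows unblinding. The minimum content in 8.3 is conditional on a narrative report, and the SAE form is not in the documents, so what it captures and when cannot be checked.
- **The roles are not equated.** Section 6.11 unblinds providers, 8.3 asks the investigator, and 8.5 does not say who judges relatedness for the rule.
- **The two kinds of relatedness differ.** Section 8.5 counts events related to the study, which includes the tube-feeding taper and its expected weight loss. An event in a placebo child can count even when the arm is known. The reports in 8.3.2 concern association with the drug.
- **Seriousness is not grade.** A grade 3 event that meets no seriousness criterion triggers no unblinding under this text.
- **No planned analysis is shown to be affected.** Aim 2 is descriptive and rests on morning cortisol, and no by-arm comparison of related SAEs is specified. All events are logged and go to the lead investigator and medical monitor whatever their attribution. The DSMB reviews all safety data, and a restart needs agreement between the investigators and the DSMB.

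All of this stands, and it limits the point to what may happen and to a subset of events. It does not close the gap. Logging every event does not mask the judgement of relatedness, and agreement on a restart comes only after the rule has already been applied.

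**Conclusion.** The point holds in a limited form. Followed as written, the plan permits relatedness of an SAE to be judged with the arm known, because 6.11 unblinds at any SAE, 8.3, 8.3.1 and 8.4 put the assessment and the code break in one reporting window, and nothing fixes their order or names a masked assessor. The reach is SAEs after dosing starts: their 7- and 15-day reports, and those 8.5 events that are also serious. It does not reach SAEs before the first dose or non-serious grade 3 events.

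No magnitude is claimed. Any trigger probability for 8.5 would rest wholly on assumed event and attribution rates, and its direction would depend on which arm's attribution is assumed to move. The conclusion assumes only that the judging investigator may be among the unblinded providers, or may be told the arm by them. This is a cheap safeguard against bias, not evidence that the safety conclusions would be wrong. Separately, 6.11 conflicts with 5.3 and 5.6 on who stays blinded. No view is taken on whether an SAE should lead to unblinding or removal.

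**What to change.** In 8.3.1 and 8.4:

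1. Require severity grade and relatedness to be recorded and time-stamped on the SAE form before the code is opened.
2. Where the code was needed first, have an assessor who has not been told the arm make the judgement. The medical monitor could do this if sent the narrative without the assignment.
3. Record any later opinion given with the arm known in a separate field.

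In 8.5, name who judges relatedness, and state that the stopping rules and any by-arm tabulation of related events use the masked assessment. Reconcile 6.11 with 5.3 and 5.6, so that the protocol says in one place who is unblinded and when.

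The cost is about a paragraph of text and two fields on the SAE form. The downside is that the investigator gives a causality opinion before knowing the arm. Urgent care is not delayed, because step 2 covers cases in which the code has to be opened first.
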